9 STATISTICAL CONSIDERATIONS

9.1 Sample Size Determination

Each intervention (clinical worsening intervention and dietary sodium application) will be treated as a standalone study in this 2x2 factorial trial, so there is no need to adjust the Type I error in our sample size calculation. The primary endpoint is a composite of time to event of all-cause death, time to event of HF rehospitalization, and change in HRQOL from baseline to 12 weeks. A win ratio³⁴ will be estimated to compare the number of participants receiving the interventions who remain event free longer and have more favorable quality of life change than those not receiving the intervention. A win ratio of 1.0 indicates that both comparison groups have equivalent outcomes in terms of events and quality of life, while a win ratio > 1.0 indicates the intervention group has a favorable profile compared to the control group and < 1.0 indicates the intervention group has a unfavorable profile compared to the control group.

We hypothesize that the win ratio for the hierarchical endpoint in our pilot study will be 1.33 in favor of the clinical worsening intervention group, meaning that people receiving the intervention will be 33% more likely to experience favorable outcomes compared to the group not given the intervention. Assuming 10% dropout, 500 randomized participants (250 per main intervention arm) provides 80% power to show a win ratio of 1.30 (56.6% winners in the intervention group excluding ties) assuming a two-sided 5% type-one error rate). 34-36 Figure 3 shows the sample size calculation for different win ratios at 80% power. After dropout, 225 participants per arm will have completed the study, producing 50,400 (225 x 224) permutations of paired comparisons. Identical reasoning is applied to the power and sample size necessary for the analysis of the dietary intervention.

A mediation analysis using structural equation modeling will be used to determine the proximal effect of the mobile phone apps results (M), "clinical worsening" and "dietary sodium intake". Assuming 10% dropout, and an alpha of 0.05, this study's 500 participants will provide at least 80% power to detect either a small standard effect size (0.14) on the association between each intervention and the proximal outcomes, and a medium effect size (0.39) on the association between proximal and distal outcomes, or a medium effect of each intervention on proximal results and a small effect on the association between proximal and distal outcomes.³⁷

There is insufficient power to detect an interaction effect of both interventions relative to the control. However, this effect will be estimated as an exploratory analysis.

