9.3.2 ANALYSES OF PRIMARY AND SECONDARY ENDPOINTS

There are two primary hypotheses for the 2x2 factorial study that investigate the main effects of each of the 2 interventions:

- 1. The use of the clinical worsening intervention will reduce deaths and HF readmissions and improve health-related quality of life compared to not using the intervention.
- 2. The use of the dietary sodium intervention will reduce deaths and HF readmissions and improve health-related quality of life compared to not using the intervention.

Note that all analyses will be conducted separately for each mobile app intervention.

The primary outcome is a composite of death, HF readmission, and change in quality of life using the win ratio method, which incorporates a hierarchy of clinical prioritization on event occurrence. We do not expect an intervention effect on death but are including the event because of its importance using this methodology. Following the unmatched pairs win ratio method of Finkelstein and Schoenfeld, $^{34-36}$ each participant receiving intervention will be compared to each participant not receiving intervention, resulting in $N_i \times N_{ni}$ pairwise comparisons, where N_i is the sample size for the intervention arm, and N_{ni} is the sample size for the non-intervention arm. For each comparison, "winners" will be determined according to Table 2, starting with scenario 1.

Scenario	Time to all-cause death	Time to HF readmission	Change in MLHFQ	Win/loss
1	Low			Loss
'	High			Win
2	Tie or both	Low		Loss
2	alive	High		Win
			Comparator	Loss
3	Tie or both alive	Tie or both not hospitalized	12-week change >=5 points better than comparator	Win
			Comparator	Tied
4	Tie or both alive	Tie or both not hospitalized	12-week change within 5 points of comparator's 12- week change	Tied

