Within each pairing, the participant with the longest survival time is counted as the "winner" of that pairing. The win ratio is the number winners divided by the number of losers associated with the intervention. The estimate of the win ratio will be calculated, and its 95% confidence interval will be calculated using bootstrap methods. The test for intervention effect is a nonparametric rank sum test. In the event there is more than a 10% loss-to-follow-up, sensitivity analyses based on multiple imputation of the primary outcome will be conducted. However, if some lost or withdrawn participants were readmitted to hospital, a determination may still be possible for the win ratio statistic.

For secondary endpoints, individual components of the composite outcome will be examined, using survival methods for time-to-event outcomes, and linear mixed effects models or piecewise linear regression for longitudinal continuous outcomes (e.g., MLHFQ). The proportion of participants experiencing 30-day readmissions will be analyzed using logistic regression. Number and percent of days alive and out of hospital (DAOH) will be analyzed using linear regression.³⁹ Repeated measures proportional odds logistic regression⁴⁰ will be used to compare NYHA classifications (ordinal measurements).²⁷ If the proportionality assumption does not hold, the outcome will be dichotomized and a generalized linear mixed model will be used.

For the primary analysis, the following stratification factors will be explored: site, sex, race, and HF type (HFpEF versus HFrEF). For the secondary analyses, the same stratification factors will be explored, and multivariable models will be fit adjusted for the same variables. A subgroup analysis will be conducted to examine intervention effects by cognition and depression status. In addition, we will explore whether there is a signal for an interaction effect for the use of both mobile applications.

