We hypothesize that the win ratio for the hierarchical endpoint in our pilot study will be 1.33 in favor of the clinical worsening intervention group, meaning that people receiving the intervention will be 33% more likely to experience favorable outcomes compared to the group not given the intervention. Assuming 10% dropout, 500 randomized participants (250 per main intervention arm) provides 80% power to show a win ratio of 1.30 (56.6% winners in the intervention group excluding ties) assuming a two-sided 5% type-one error rate).³⁴⁻³⁶ Figure 3 shows the sample size calculation for different win ratios at 80% power. After dropout, 225 participants per arm will have completed the study, producing 50,400 (225 x 224) permutations of paired comparisons. Identical reasoning is applied to the power and sample size necessary for the analysis of the dietary intervention.

A mediation analysis using structural equation modeling will be used to determine the proximal effect of the mobile phone apps results (M), “clinical worsening” and “dietary sodium intake”. Assuming 10% dropout, and an alpha of 0.05, this study’s 500 participants will provide at least 80% power to detect either a small standard effect size (0.14) on the association between each intervention and the proximal outcomes, and a medium effect size (0.39) on the association between proximal and distal outcomes, or a medium effect of each intervention on proximal results and a small effect on the association between proximal and distal outcomes.³⁷

There is insufficient power to detect an interaction effect of both interventions relative to the control.

8 General Analysis Considerations

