8.1 Timing of Analyses

The final analyses of the ManageHF study were to be performed after all enrolled participants have completed study follow-up. The ManageHF study was prematurely terminated by the Data Safety and Data Monitoring (DSMB) Committee owing to insufficient enrollment.

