			12-week change within 5 points of comparator's 12-week change	Tied

Within each pairing, the participant with the longest survival time is counted as the "winner" of that pairing. The win ratio is the number winners divided by the number of losers associated with the intervention. The estimate of the win ratio will be calculated, and its 95% confidence interval will be calculated using bootstrap methods. The test for intervention effect is a nonparametric rank sum test. In the event there is more than a 10% loss-to-follow-up, sensitivity analyses based on multiple imputation of the primary outcome will be conducted. However, if some lost or withdrawn participants were readmitted to hospital, a determination may still be possible for the win ratio statistic.

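### The stated 80% power for a win ratio of 1.30 does not belong to the planned test: 225 completers per arm give about 67–68% with no ties, and less with ties

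*Protocol*

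**What the plan says.** Protocol 9.1 gives the sample size basis, and SAP section 7 repeats it: two-sided 5% error, 10% dropout and 225 completers per arm, so that "500 randomized participants (250 per main intervention arm) provides 80% power to show a win ratio of 1.30". The same effect is also expressed as "56.6% winners in the intervention group excluding ties". The claim extends to the second intervention: "Identical reasoning is applied to the power and sample size necessary for the analysis of the dietary intervention". A win ratio of 1.33 is hypothesised, but the 80% is attached to 1.30.

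The primary analysis is set out in Protocol 9.3.2 and in SAP 8.3 and 10.2. It is unmatched: "each participant receiving intervention will be compared to each participant not receiving intervention". On the test, the protocol says: "The test for intervention effect is a nonparametric rank sum test". In the win/loss table, two participants who are level on death and HF readmission tie if one has a "12-week change within 5 points of" the other's.

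Neither text names a power formula or a tie proportion. Both point to Figure 3 and to published win ratio references.

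**The concern.** In an unmatched comparison each participant enters many pairs, so the pairwise results are correlated and the number of participants is not a number of independent wins and losses. Power has to come from the variance of the rank sum or win ratio statistic. The figures 56.6%, 450 and 80% fit together closely under a simple binomial calculation, which suggested that the stated power might belong to a different test.

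At stake is the chance of missing the target effect at full planned enrolment, in both primary comparisons. The SAP records that the trial stopped "owing to insufficient enrollment", yet section 7 repeats the 80% without qualification. A reader weighing an inconclusive result could be misled about what the design could have detected.

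**Working it through.** **Inputs (Protocol 9.1; SAP section 7).** Two-sided alpha 0.05, z = 1.960. Power 80%, z = 0.8416. (1.960 + 0.8416)² = 7.849. Completers: 250 × 0.9 = 225 per arm, N = 450. Win ratio 1.30 means p = 1.30/2.30 = 0.5652 winners excluding ties. The plan's 56.6% corresponds to 0.566/0.434 = 1.304. Both are carried through.

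**Reproducing the 80%.** Treat completers as independent wins or losses, with p = 0.566.
- One sample, 56.6% against 50%: N = (1.960 × 0.5 + 0.8416 × √(0.566 × 0.434))² / 0.066² = 448 in total. Power at 450 is 80.2%.
- Two samples, 56.6% against 43.4%: 224 per arm. Power at 225 per arm is 80.2%.
- At exactly 0.5652 the same formulas need 459 in total and 230 per arm, and give 79.2%.

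These match the stated design, but neither is the planned test.

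**The planned test, no ties.**

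*Noether formula for the rank sum test, equal arms:* power = Φ((p − 0.5)√(3N) − 1.960).
- p = 0.5652: Φ(0.0652 × √1350 − 1.960) = Φ(2.396 − 1.960) = 66.9%. N for 80% = 7.849/(3 × 0.0652²) = 615.
- p = 0.566: Φ(2.425 − 1.960) = 67.9%. N for 80% = 601.

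*Log win ratio, equal arms:* variance = (16/3)/N; power = Φ(ln(WR)/√(5.333/N) − 1.960).
- WR 1.30: Φ(0.2624/√(5.333/450) − 1.960) = Φ(2.410 − 1.960) = 67.4%. N for 80% = 5.333 × 7.849/0.2624² = 608.
- WR 1.304: 68.4%. N for 80% = 594.

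*Simulation:* two-sided rank sum test, 225 per arm, normal shift, 40,000 trials per setting. Power is 66.9% at p = 0.5652 and 68.1% at p = 0.566.

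**More generous readings of the planned test, two-sided, no ties.**

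| Reading | Power |
|---|---|
| WR 1.30, all 500 analysed | 71.4–71.9% |
| 56.6% winners, all 500 analysed | 72.5–73.0% |
| WR 1.33, 450 analysed | 74.0–74.5% |
| WR 1.33, all 500 analysed | 78.3–78.9% |

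None reaches 80%.

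**Ties.** The documents give no tie proportion and no standard deviation for the MLHFQ change, so the proportions below are assumptions. With a proportion t of tied pairs, the log win ratio variance is multiplied by (1 + t)/(1 − t). The detectable win ratio at 80% power is exp(2.8016 × √(5.333 × (1 + t)/(1 − t)/450)).

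| Tied pairs (assumed) | Variance factor | Power at WR 1.30, N = 450 | WR detectable at 80% |
|---|---|---|---|
| 0% | 1.00 | 67% | 1.36 |
| 5% | 1.11 | 63% | 1.38 |
| 10% | 1.22 | 59% | 1.40 |
| 20% | 1.50 | 50% | 1.45 |

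A separate simulation, with a tie threshold and the win ratio held at 1.30, also showed power falling as ties increase: 60% at 8% ties, 52% at 18%.

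**Pair count.** The plan describes 225 per arm as "producing 50,400 (225 x 224) permutations of paired comparisons". Under its own rule of multiplying the two arm sizes, the count is 225 × 225 = 50,625. This slip does not cause the power gap.

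**The case against.** The strongest objection is about consequence. The trial ended early, so the design with 225 per arm was never carried out, and nothing in the analysis uses the 80%. That is right, and it limits the matter to a wrong statement of a design property. The statement is still wrong as written, and the SAP repeats it after the stop without listing it among the differences in section 14.

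Second, Figure 3 and the authors' formula cannot be seen. The binomial origin is therefore only a plausible explanation, and it fits best with the rounded 56.6%. The conclusion does not depend on it: the inputs and the test are stated, and those inputs do not give 80% for that test.

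Third, the intention-to-treat set holds all randomized participants, and record review may allow some who drop out to be classified. Effective N may therefore lie between 450 and 500, with power of about 67–73% before ties. This stands, and it still falls short of 80%.

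Fourth, the tie figures are illustrative. Their direction is secure when the win ratio is fixed, but the individual values should not carry weight.

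Finally, silently rewriting an approved protocol after termination would blur the record. That bears on how the correction is made, not on whether it is needed.

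**Conclusion.** The concern holds. On the plan's own inputs, the planned rank sum test has 66.9–67.4% power at a win ratio of 1.30 and 67.9–68.4% at 56.6% winners, not 80%. The chance of missing the target effect at 450 completers is about 32–33% rather than 20%, in each of the two primary comparisons. Power of 80% needs about 594–615 completers or a win ratio of about 1.36. These figures assume equal arms and no ties, which is the favourable case. Counting all 500 as analysable raises power to at most about 73% at the stated effect. No estimate, test or confidence interval is affected.

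**What to change.** In SAP section 7 and Protocol 9.1, replace the power statement with wording such as: with 225 completers per arm, the planned unmatched rank sum test has about 67–68% power at two-sided 5% for a win ratio of 1.30 (56.6% winners) if no pairs tie, and less with ties; 80% power corresponds to a win ratio of about 1.36 or more. Apply the same correction to the dietary sodium comparison. State the formula behind the 80% and any tie proportion that was assumed. Say that design-stage power does not describe the terminated trial. Correct the pair count to 50,625.

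Make the protocol correction as a dated erratum and record the change in SAP section 14, so that the approved text stays traceable. The cost is wording only, and a less favourable stated power. No further patients and no change to any analysis are needed.

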9.2 POPULATIONS FOR ANALYSES

All randomized participants will be included in the intent-to-treat (ITT) population, which is the analysis set used in all treatment comparisons of primary and secondary outcomes. All randomized participants who received an intervention (safety population) will be included in safety analyses.

9.3 STATISTICAL ANALYSES

9.3.1 GENERAL APPROACH

The number of expected participants, the expected effect size, the power and the statistical methods for the clinical trial adequately address the factorial design study's hypotheses. As each primary analysis will be for an independent hypothesis concerning each individual intervention, there will be no multiplicity for corresponding statistical tests, and statistical tests with a two-sided p-value <0.05 will be considered statistically significant. Secondary and tertiary analyses are considered hypothesis-generating and will also not incorporate any adjustments for multiplicity. Analyses will be performed using SAS software (SAS Institute, Inc., Cary, NC) or R freeware. ³⁸ A statistical analysis plan (SAP) will be written for the study that contains detailed descriptions of the analyses to be performed; it will be finalized prior to the database lock.

9.3.2 ANALYSES OF PRIMARY AND SECONDARY ENDPOINTS

There are two primary hypotheses for the 2x2 factorial study that investigate the main effects of each of the 2 interventions:

- 1. The use of the clinical worsening intervention will reduce deaths and HF readmissions and improve health-related quality of life compared to not using the intervention.
- 2. The use of the dietary sodium intervention will reduce deaths and HF readmissions and improve health-related quality of life compared to not using the intervention.

Note that all analyses will be conducted separately for each mobile app intervention.

The primary outcome is a composite of death, HF readmission, and change in quality of life using the win ratio method, which incorporates a hierarchy of clinical prioritization on event occurrence. We do not expect an intervention effect on death but are including the event because of its importance using this methodology. Following the unmatched pairs win ratio method of Finkelstein and Schoenfeld, $^{34-36}$ each participant receiving intervention will be compared to each participant not receiving intervention, resulting in $N_i \times N_{ni}$ pairwise comparisons, where N_i is the sample size for the intervention arm, and N_{ni} is the sample size for the non-intervention arm. For each comparison, "winners" will be determined according to Table 2, starting with scenario 1.

Scenario	Time to all-cause death	Time to HF readmission	Change in MLHFQ	Win/loss
1	Low			Loss
'	High			Win
2	Tie or both	Low		Loss
2	alive	High		Win
			Comparator	Loss
3	Tie or both alive	Tie or both not hospitalized	12-week change >=5 points better than comparator	Win
			Comparator	Tied
4	Tie or both alive	Tie or both not hospitalized	12-week change within 5 points of comparator's 12- week change	Tied

Within each pairing, the participant with the longest survival time is counted as the "winner" of that pairing. The win ratio is the number winners divided by the number of losers associated with the intervention. The estimate of the win ratio will be calculated, and its 95% confidence interval will be calculated using bootstrap methods. The test for intervention effect is a nonparametric rank sum test. In the event there is more than a 10% loss-to-follow-up, sensitivity analyses based on multiple imputation of the primary outcome will be conducted. However, if some lost or withdrawn participants were readmitted to hospital, a determination may still be possible for the win ratio statistic.

For secondary endpoints, individual components of the composite outcome will be examined, using survival methods for time-to-event outcomes, and linear mixed effects models or piecewise linear regression for longitudinal continuous outcomes (e.g., MLHFQ). The proportion of participants experiencing 30-day readmissions will be analyzed using logistic regression. Number and percent of days alive and out of hospital (DAOH) will be analyzed using linear regression.³⁹ Repeated measures proportional odds logistic regression⁴⁰ will be used to compare NYHA classifications (ordinal measurements).²⁷ If the proportionality assumption does not hold, the outcome will be dichotomized and a generalized linear mixed model will be used.

For the primary analysis, the following stratification factors will be explored: site, sex, race, and HF type (HFpEF versus HFrEF). For the secondary analyses, the same stratification factors will be explored, and multivariable models will be fit adjusted for the same variables. A subgroup analysis will be conducted to examine intervention effects by cognition and depression status. In addition, we will explore whether there is a signal for an interaction effect for the use of both mobile applications.

9.3.3 ANALYSES OF SECONDARY ENDPOINTS: PROXIMAL OUTCOMES

For Aim 2, we hypothesize that that each intervention, "clinical worsening – time in yellow and red" for the clinical worsening intervention and "measurement of dietary sodium intake" for the dietary sodium intervention is an intermediate outcome, with a significant association with the intervention, and significant association with a composite endpoint of death, hospitalization and 12-week MLHFQ decline.

Mediation analysis will be used to discern the strength of these measurements as proximal outcomes.^{37,41} Structural equation modelling will be used to estimate the effect of each interventions proximal results (M), on the relationship between the mobile app interventions (X) on the distal outcomes (Y) of adverse heart failure outcomes and quality of life. In particular, we will estimate the effect of "clinical worsening – time in yellow and red" (M) on the relationship between the clinical worsening intervention (X) and clinical and quality of life outcomes (Y), and the effect of "measurement of dietary sodium intake" (M) on the relationship between the dietary sodium intervention (X) and the clinical and quality of life outcomes (Y). The structural equation model will consist of a statement on the association between the intervention (X) on the proximal outcome (M), and a statement on the association between (X) and (M) on (Y), assuming error terms are uncorrelated. Structural equation modelling will be used rather than widely used standard regression techniques such as those proposed in Baron and Kenny Causal Steps because it provides more power to detect an effect, and because it acknowledges the role of the proximal outcome as both an effect of the intervention and a cause of the distal outcome.^{42,43} Both clinical outcomes and quality of life outcomes will be used to explore the assessment of the proximal outcomes as mediators.

As secondary analyses, we will conduct the same mediation analysis using the individual components of the composite endpoint. As exploratory analysis, we will conduct all the above analyses stratifying by race and gender.

